#### 7.1.5.4 Survival Status

To ensure current and complete survival data is available at the time of database locks, updated survival status may be requested during the course of the study by the Sponsor. For example, updated survival status may be requested prior to but not limited to an interim and/or final analysis. Upon Sponsor notification, all subjects who do not/will not have a scheduled study visit or study contact during the Sponsor-defined time period will be contacted for their survival status (excluding subjects that have a previously recorded death event in the collection tool).

Visit requirements are outlined in Section 6.0 - Trial Flow Chart.

### 7.2 Assessing and Recording Adverse Events

An adverse event is defined as any untoward medical occurrence in a patient or clinical investigation subject administered a pharmaceutical product and which does not necessarily have to have a causal relationship with this treatment. An adverse event can therefore be any unfavorable and unintended sign (including an abnormal laboratory finding, for example), symptom, or disease temporally associated with the use of a medicinal product or protocol-specified procedure, whether or not considered related to the medicinal product or protocol-specified procedure. Any worsening (i.e., any clinically significant adverse change in frequency and/or intensity) of a preexisting condition that is temporally associated with the use of the Sponsor's product, is also an adverse event.

Changes resulting from normal growth and development that do not vary significantly in frequency or severity from expected levels are not to be considered adverse events. Examples of this may include, but are not limited to, teething, typical crying in infants and children and onset of menses or menopause occurring at a physiologically appropriate time.

Sponsor's product includes any pharmaceutical product, biological product, device, diagnostic agent or protocol-specified procedure, whether investigational (including placebo or active comparator medication) or marketed, manufactured by, licensed by, provided by or distributed by the Sponsor for human use.

Adverse events may occur during clinical trials, or as prescribed in clinical practice, from overdose (whether accidental or intentional), from abuse and from withdrawal.

All adverse events that occur after the subject provides documented informed consent but before treatment allocation/randomization must be reported by the investigator if they cause the subject to be excluded from the trial, or are the result of a protocol-specified intervention, including but not limited to washout or discontinuation of usual therapy, diet, placebo treatment or a procedure. From the time of treatment allocation/randomization through 30 days following cessation of treatment, all adverse events must be reported by the investigator. Such events will be recorded at each examination on the Adverse Event case report forms/worksheets. The reporting timeframe for adverse events meeting any serious criteria is described in section 7.2.3.1. The investigator will make every attempt to follow all subjects with non-serious adverse events for outcome.

Electronic reporting procedures can be found in the Electronic Data Capture (EDC) data entry guidelines. Paper reporting procedures can be found in the Investigator Trial File Binder (or equivalent).

Adverse events will not be collected for subjects during the pre-screening period (for determination of archival tissue status) as long as that subject has not undergone any protocol-specified procedure or intervention. If the subject requires a blood draw, fresh tumor biopsy etc., the subject is first required to provide consent to the main study and AEs will be captured according to guidelines for standard AE reporting.

### **7.2.1 Definition of an Overdose for This Protocol and Reporting of Overdose to the Sponsor**

For purposes of this trial, an overdose will be defined as any dose exceeding the prescribed dose for pembrolizumab by at least 1000 mg (5 times the dose), 20% or more above the prescribed dose for MK-4280 or MK-4280A, and any dose above the protocol-prescribed dose of lenvatinib if associated with an adverse event. No specific information is available on the treatment of overdose of pembrolizumab, MK-4280, MK-4280A, or lenvatinib. In the event of overdose, pembrolizumab, MK-4280, MK-4280A, or lenvatinib should be discontinued and the subject should be observed closely for signs of toxicity. Appropriate supportive treatment should be provided if clinically indicated.

Sponsor does not recommend specific treatment for an overdose. Decisions regarding dose interruptions or modifications will be made by the investigator in consultation with the Sponsor Clinical Director based on the clinical evaluation of the participant.

There is no specific antidote for an overdose of lenvatinib. Due to its high degree of plasma protein binding, lenvatinib is not expected to be dialyzable. Adverse reactions in patients receiving single doses of lenvatinib as high as 40 mg were similar to those in clinical studies at the recommended dose for differentiated thyroid cancer, RCC, and HCC.

Refer to the approved prescribing information and local practice guidelines regarding the definition of and treatment for an overdose of mFOLFOX7 or FOLFIRI.

If an adverse event(s) is associated with (“results from”) the overdose of Sponsor's product or vaccine, the adverse event(s) is reported as a serious adverse event, even if no other seriousness criteria are met.

If a dose of Sponsor's product or vaccine meeting the protocol definition of overdose is taken without any associated clinical symptoms or abnormal laboratory results, the overdose is reported as a non-serious Event of Clinical Interest (ECI), using the terminology “accidental or intentional overdose without adverse effect.”

All reports of overdose with and without an adverse event must be reported by the investigator within 24 hours to the Sponsor either by electronic media or paper. Electronic reporting procedures can be found in the EDC data entry guidelines. Paper reporting procedures can be found in the Investigator Trial File Binder (or equivalent).

### **7.2.1.1 Definitions of Medication Error, Misuse, and Abuse**

#### **Medication error**

This is an unintended failure in the drug treatment process that leads to or has the potential to lead to harm to the patient.

#### **Misuse**

This refers to situations where the medicinal product is intentionally and inappropriately used not in accordance with the terms of the product information.

#### **Abuse**

This corresponds to the persistent or sporadic, intentional excessive use of a medicinal product for a perceived psychological or physiological reward or desired nontherapeutic effect.

### **7.2.2 Reporting of Pregnancy and Lactation to the Sponsor**

Although pregnancy and lactation are not considered adverse events, it is the responsibility of investigators or their designees to report any pregnancy or lactation in a subject (spontaneously reported to them) that occurs during the trial.

Pregnancies and lactations that occur after the subject provides documented informed consent but before treatment allocation/randomization must be reported by the investigator if they cause the subject to be excluded from the trial, or are the result of a protocol-specified intervention, including but not limited to washout or discontinuation of usual therapy, diet, placebo treatment or a procedure. Pregnancies and lactations that occur from the time of treatment allocation/randomization through 120 days following cessation of study treatment (or 30 days following cessation of study treatment if the subject initiates new anticancer therapy, whichever is earlier) must be reported by the investigator. All reported pregnancies must be followed to the completion/termination of the pregnancy. Pregnancy outcomes of spontaneous abortion, missed abortion, benign hydatidiform mole, blighted ovum, fetal death, intrauterine death, miscarriage and stillbirth must be reported as serious events (Important Medical Events). If the pregnancy continues to term, the outcome (health of infant) must also be reported.

Such events must be reported within 24 hours to the Sponsor either by electronic media or paper. Electronic reporting procedures can be found in the EDC data entry guidelines. Paper reporting procedures can be found in the Investigator Trial File Binder (or equivalent).

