Absolute neutrophil count (ANC)	$\geq 1500/\text{mcL}$ without growth factor dependency (including erythropoietin (EPO), granulocyte-colony stimulating factor (G-CSF), or platelet derived growth factor (PDGF) stimulating agents) within 7 days of assessment
Platelets	$\geq 100,000/\text{mcL}$
Hemoglobin	$\geq 9 \text{ g/dL}$ or $\geq 5.6 \text{ mmol/L}$ without transfusion or EPO dependency (within 7 days of assessment)
Renal	
Creatinine OR Measured or calculated creatinine clearance (glomerular filtration rate [GFR] can also be used in place of creatinine or creatinine clearance [CrCl])	$\leq 1.5 \times \text{ upper limit of normal (ULN)}$ OR $\geq 60 \text{ mL/min}$ for subject with creatinine levels $>1.5 \times$ institutional ULN Note: Creatinine clearance should be calculated per institutional standard
Hepatic	
Total Bilirubin	$\leq 1.5 \times \text{ ULN}$ OR Direct bilirubin $\leq \text{ULN}$ for subjects with total bilirubin levels $>1.5 \text{ ULN}$
Aspartate aminotransferase (AST) (serum glutamic oxaloacetic transaminase [SGOT]) and Alanine aminotransferase (ALT) (serum glutamic-pyruvic transaminase [SGPT])	$\leq 2.5 \times \text{ ULN}$ OR $\leq 5 \text{ X ULN}$ for subjects with liver metastases
Coagulation	
International Normalized Ratio (INR) or Prothrombin Time (PT)	$\leq 1.5 \times \text{ ULN}$ unless the subject is receiving anticoagulant therapy
Activated Partial Thromboplastin Time (aPTT) or Partial Thromboplastin Time (PTT)	$\leq 1.5 \times \text{ ULN}$ unless the subject is receiving anticoagulant therapy

6. A female subject is eligible to participate if she is not pregnant or breastfeeding, and at least one of the following conditions applies:

- Is not a WOCBP

OR

- Is a WOCBP and using a contraceptive method that is highly effective (with a failure rate of  $<1\%$  per year), with low user dependency, or be abstinent from heterosexual intercourse as their preferred and usual lifestyle (abstinent on a long term and persistent basis), as described in Section 12.8 during the intervention period and for at least 180 days after the last dose of chemotherapy, 120 days after the last dose of pembrolizumab or MK-4280, or 30 days after the last dose of lenvatinib, whichever occurs last. The investigator should evaluate the potential

for contraceptive method failure (ie, noncompliance, recently initiated) in relationship to the first dose of study intervention.

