- **Arm 3 and Arm 4 only:** WOCBP must also agree not to donate eggs (ova, oocytes) to others or freeze/store for her own use for the purpose of reproduction during and for at least 180 days after the last dose of chemotherapy.
- A WOCBP must have a negative highly sensitive pregnancy test (urine or serum as required by local regulations) within 72 hours before the first dose of study intervention.

**Arm 6 only:** A WOCBP must have a negative highly sensitive pregnancy test (urine or serum as required by local regulations) within 24 hours before the first dose of study intervention.

- If a urine test cannot be confirmed as negative (eg, an ambiguous result), a serum pregnancy test is required. In such cases, the participant must be excluded from participation if the serum pregnancy result is positive.
- Abstain from breastfeeding during the study intervention period and for at least 180 days after the last dose of chemotherapy, 120 days after the last dose of pembrolizumab or MK-4280, or 30 days after the last dose of lenvatinib, whichever occurs last.
- Additional requirements for pregnancy testing during and after study intervention are located in Section 7.1.2.7.
- The investigator is responsible for review of medical history, menstrual history, and recent sexual activity to decrease the risk for inclusion of a woman with an early undetected pregnancy.
- Contraceptive use by women should be consistent with local regulations regarding the methods of contraception for those participating in clinical studies.
- If the contraception requirements in the local label for any of the study drugs is more stringent than the requirements above, the local label requirements should be followed.

7. Male subjects are eligible to participate if they agree to the following during the intervention period and for at least 95 days after the last dose of chemotherapy or 7 days after the last dose of lenvatinib, whichever occurs last:

- Be abstinent from heterosexual intercourse as their preferred and usual lifestyle (abstinent on a long term and persistent basis) and agree to remain abstinent  
OR
- Must agree to use contraception unless confirmed to be azoospermic (vasectomized or secondary to medical cause Section 12.8) as detailed below:

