### **5.7.4 Use in Pregnant Women**

If a subject inadvertently becomes pregnant while on study treatment, the subject will immediately be removed from the study. The site will contact the subject at least monthly and document the subject's status until the pregnancy has been completed or terminated. The outcome of the pregnancy will be reported to the Sponsor within 24 hours if the outcome is a serious adverse experience (eg, death, abortion, congenital anomaly, or other disabling or life-threatening complication to the mother or newborn). The study investigator will make every effort to obtain permission to follow the outcome of the pregnancy and report the condition of the fetus or newborn to the Sponsor. If a male subject impregnates his female partner the study personnel at the site must be informed immediately and the pregnancy reported to the Sponsor and followed as described above and in Section 7.2.2.

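### The dated pregnancy and lactation reporting rule in 7.2.2 is shorter than the precaution windows in 5.1.2, and is not reconciled with the undated duty that opens 7.2.2

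*Combined protocol and SAP*

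**What the plan says.** **Reporting (7.2.2).** The section opens with a general responsibility that has no day limit: investigators are "to report any pregnancy or lactation in a subject (spontaneously reported to them) that occurs during the trial". It then gives a dated obligation for every arm, running from allocation "through 120 days following cessation of study treatment", with a shorter alternative: "or 30 days following cessation of study treatment if the subject initiates new anticancer therapy, whichever is earlier) must be reported by the investigator". It makes no separate provision for the chemotherapy arms. The duty to follow a pregnancy to its end attaches to pregnancies that have been reported.

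**Precautions for women (5.1.2, criterion 6).** Contraception is required "for at least 180 days after the last dose of chemotherapy, 120 days after the last dose of pembrolizumab or MK-4280", or 30 days after lenvatinib, with the latest of these dates governing. The breastfeeding restriction uses the same periods: "Abstain from breastfeeding during the study intervention period and for at least 180 days after the last dose of chemotherapy". Women in Arms 3 and 4 must also not donate or store eggs "during and for at least 180 days after the last dose of chemotherapy".

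**Men and partners.** Criterion 7 of 5.1.2 asks men to take precautions "for at least 95 days after the last dose of chemotherapy", or 7 days after lenvatinib if later. Section 5.7.4 sends partner pregnancies to the same reporting section: the site must be told and "the pregnancy reported to the Sponsor and followed as described above and in Section 7.2.2".

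**The concern.** A contraception window and a pregnancy-reporting window normally serve the same purpose. The first asks patients to avoid conception while exposure may still matter; the second makes sure the sponsor learns of any pregnancy that happens anyway. Here the second can close before the first.

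A site that follows the dated sentence could treat a pregnancy on day 150 after the last dose in Arm 3 as not reportable, although the patient was still under the protocol's contraception requirement. Because follow-up depends on reporting, the outcome could be lost too. Safety and tolerability are the primary objective for Arms 3 and 4 (Section 3.1), and Section 4.2.1.1 states that there were no clinical safety data for the combination with chemotherapy.

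The protocol does link pregnancy surveillance to the precaution window elsewhere, but only for Arm 6. Section 7.1.2.7 ties the end-of-exposure test to the contraception time frame in 5.1.2. The Arm 6 text in Appendix 12.8 continues testing for 120 days whether or not new anticancer therapy has begun. A pregnancy found by that testing after new therapy could still fall outside the dated rule in 7.2.2.

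**Working it through.** The documents give no figure for this gap, so there is nothing to reproduce. The check is a subtraction of windows, with all days counted from the last dose of any study treatment.

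**Inputs**
- Reporting end, no new therapy: day 120 (7.2.2)
- Reporting end, new therapy: day 30 (7.2.2)
- Precaution for women: 180 days after chemotherapy; 120 days after pembrolizumab or MK-4280 (5.1.2, criterion 6)
- Precaution for men in Arms 3 and 4: 95 days after chemotherapy (5.1.2, criterion 7)
- L: days by which the last chemotherapy dose precedes the last dose of any agent. The documents give no value, so a range is shown. L matters because the reporting clock starts at the end of study treatment while the 180 days start at the last chemotherapy dose, and Section 5.2.6 lets agents be held separately.

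**Formula.** Shortfall = max(0, precaution end − reporting end).

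**Women, Arms 3 and 4.** Taking an antibody as the last agent when L > 0, the precaution ends on day max(180 − L, 120). The shortfall is then:
- no new therapy: max(180 − L, 120) − 120 = max(0, 60 − L)
- new therapy: max(180 − L, 120) − 30 = max(90, 150 − L)

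| L (days) | Precaution ends (day) | Shortfall, no new therapy | Shortfall, new therapy |
|---|---|---|---|
| 0 | 180 | 60 | 150 |
| 7 | 173 | 53 | 143 |
| 21 | 159 | 39 | 129 |
| 30 | 150 | 30 | 120 |
| 60 or more | 120 | 0 | 90 |

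**Women, arms with pembrolizumab or MK-4280 and no chemotherapy.** No new therapy: 120 − 120 = 0. New therapy: 120 − 30 = 90, taking the antibody as the last agent stopped.

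**Partners of men, Arms 3 and 4, at L = 0.** No new therapy: max(0, 95 − 120) = 0. New therapy: 95 − 30 = 65.

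Without new therapy, then, only women in Arms 3 and 4 are affected. With new therapy the mismatch reaches every arm that contains pembrolizumab or MK-4280.

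**The case against.** The strongest reply is that a reader might infer that no reporting duty at all exists after day 120. The documents do not support that. The opening sentence of 7.2.2 covers any pregnancy or lactation spontaneously reported during the trial, with no day limit. Section 7.1.5.3.2 keeps patients in contact about every 12 weeks after progression or new therapy, so a woman on day 150 will normally still be in the trial. In Arms 3 and 4 the flow chart in Section 6.2 shows pregnancy tests only at Screening and Cycle 1 Day 1, so a late pregnancy would probably surface by exactly that route. This stands in part: the accurate complaint is that one section holds an undated general duty and a shorter dated obligation, and does not say which governs.

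Second, serious outcomes have a backstop. Table 9 makes a congenital anomaly a serious event regardless of when it is diagnosed, and 7.2.3.1 requires related serious events to be reported even outside the normal window. This is only partial cover. An uncomplicated pregnancy is not a serious event. The late route also requires attribution to the Sponsor's product, and chemotherapy sourced by the site may not meet that definition.

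Third, 60 days is tempting as a fixed figure. It is a maximum, as the table shows.

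Fourth, it is tempting to call the 120 days an oversight that was simply not extended for chemotherapy. The amendment history is blacked out, no passage says that reporting must match contraception, and 7.2.3.1 uses the same 30-day truncation for serious adverse events. The cause cannot be established; the mismatch can.

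Finally, the numbers are small. Section 2.1.2 plans up to 20 patients in each of Arms 3 and 4, and only some will be women who can conceive. That limits the weight of the point without removing it.

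**Conclusion.** The inconsistency is real and concerns safety reporting only. Sample size, error rates, analysis populations and efficacy estimates are untouched.

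The dated rule falls short of the precaution windows by:
- up to 60 days for women in Arms 3 and 4 without new therapy, and up to 150 days with it
- up to 90 days with new therapy for women in the arms with pembrolizumab or MK-4280 and no chemotherapy
- up to 65 days with new therapy for partners of men in Arms 3 and 4

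These maxima rest on three assumptions. The agent that sets the precaution window is among the last stopped. The 30-day cut-off applies as written once new therapy has started. The term study treatment in 7.2.2 includes chemotherapy, although Table 3 labels it background therapy.

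The documents do not support saying that late pregnancies carry no duty of any kind, or that the problem is confined to Arms 3 and 4. They support saying that a site following the dated rule could leave unreported, and not followed to outcome, a pregnancy inside the protocol's own precaution window.

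**What to change.** Reconcile 7.2.2 with 5.1.2 arm by arm, so that a pregnancy or lactation within the protocol's own precaution window is clearly reportable, and any such pregnancy is followed to outcome. The revision should:
- state the reporting window for each arm next to that arm's precaution window, and name the dose from which each is counted
- say how the 30-day cut-off for new anticancer therapy relates to precautions that are still running
- say how the undated opening sentence and the dated obligation fit together
- cover partner pregnancies, which 5.7.4 refers to 7.2.2

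Which window is correct is for the sponsor to decide. If reporting is meant to end before the precautions do, the protocol should say so and give the reason.

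The cost is protocol wording and very few extra reports. Patients are already contacted about every 12 weeks in survival follow-up, so no new visit is needed.

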### **7.2.3 Immediate Reporting of Adverse Events to the Sponsor**

#### **7.2.3.1 Serious Adverse Events**

A serious adverse event is any adverse event occurring at any dose or during any use of Sponsor's product that:

- Results in death;
- Is life threatening;

- Results in persistent or significant disability/incapacity;
- Results in or prolongs an existing inpatient hospitalization;
- Is a congenital anomaly/birth defect;
- Is an other important medical event.

**Note:** In addition to the above criteria, adverse events meeting either of the below criteria, although not serious per ICH definition, are reportable to the Sponsor in the same timeframe as SAEs to meet certain local requirements. Therefore, these events are considered serious by the Sponsor for collection purposes.

- Is a new cancer (that is not a condition of the study);
- Is associated with an overdose.

Refer to [Table 9](#) for additional details regarding each of the above criteria.

Progression of the cancer under study is not considered an adverse event unless it results in hospitalization or death.

For the time period beginning when the subject provides documented informed consent until treatment allocation/randomization, any serious adverse event, or follow up to a serious adverse event, including death due to any cause, that occurs to any subject must be reported within 24 hours to the Sponsor if it causes the subject to be excluded from the trial, or is the result of a protocol-specified intervention, including but not limited to washout or discontinuation of usual therapy, diet, placebo treatment or a procedure.

For the time period beginning at treatment allocation/randomization through 90 days following cessation of study treatment (or 30 days following cessation of study treatment if the subject initiates new anticancer therapy, whichever is earlier), any serious adverse event, or follow up to a serious adverse event, including death due to any cause, whether or not related to the Sponsor's product, must be reported within 24 hours to the Sponsor either by electronic media or paper. Electronic reporting procedures can be found in the EDC data entry guidelines. Paper reporting procedures can be found in the Investigator Trial File Binder (or equivalent).

Additionally, any serious adverse event, considered by an investigator who is a qualified physician to be related to the Sponsor's product that is brought to the attention of the investigator at any time outside of the time period specified in the previous paragraph also must be reported immediately to the Sponsor.

All subjects with serious adverse events must be followed up for outcome.

